5.2.1.4. Efficacy Analysis Variables (RECIST v.1.1)

Definition of efficacy analysis variables are listed alphabetically.

Disease Control Rate (DCR) is defined as the proportion of treated patients achieving a best overall response of complete response (CR), partial response (PR), or stable disease (SD) per Response Evaluation Criteria In Solid Tumors Version 1.1 (RECIST v.1.1). Patients who do not have any postbaseline tumor response assessments for any reason are considered non-responders and are included in the denominator when calculating the response rate.

Note. Best overall response is the best response recorded from the start of treatment until disease progression, in the order of CR, PR, and SD.

Duration of Response (DoR) is defined only for responders (patients with a confirmed CR or PR). It is measured from the date of first evidence of a confirmed CR or PR to the date of objective progression or the date of death due to any cause, whichever is earlier. If a responder is not known to have died or have objective progression as of the data inclusion cutoff date, DoR will be censored at the date of the last complete objective progression-free disease assessment.

Objective response rate (ORR) is defined as the proportion of enrolled patients who have received any amount of either study drug, have at least 1 postbaseline tumor image, and achieve a best overall response of CR or PR. The ORR will be assessed based on RECIST v.1.1 (Eisenhauer et al. 2009) and immune-related RECIST (irRECIST).

Time-to-response (TTR) is defined as the time from the date of first study treatment until the first evidence of a confirmed CR or PR.

Progression-free survival (PFS) is defined as the time from the date of first study treatment until the date of the first observed radiographically documented progressive disease (PD) or death due to any cause, whichever is earlier.

Table JVDF.3 lists rules for determining date of progression or censor for PFS. The censoring is taken in the following order:

- If a patient does not have a complete baseline disease assessment, then the PFS time will be censored at the enrollment date, regardless of whether or not objectively determined disease progression or death has been observed for the patient; otherwise,
- If a patient is not known to have died or have objective progression as of the data inclusion cutoff date for the analysis, the PFS time will be censored at the last complete objective progression-free disease assessment date.

Note. If there are multiple dates associated with 1 radiological tumor assessment, the assessment date will be set to the first date when the overall response is PD and the last date otherwise. A radiological tumor assessment is considered adequate if its response is CR, PR, SD, or PD.

PFS (day) = Date of progression / censor – date of first treatment + 1

Table JVDF.3. Rules for Determining Date of Progression or Censor for Progression-Free Survival

Rule	Situation	Date of Progression or Censor	Outcome
1	No baseline tumor assessments	Date of first treatment	Censored
2	No postbaseline assessments and no death	Date of first treatment	Censored
3	No documented progression and no death (with a postbaseline tumor assessment)	Date of last adequate tumor assessment	Censored
4	Patient lost to follow-up (or withdrew consent from study participation) before documented progression or death	Date of last adequate tumor assessment	Censored
5	Documented progression	Date of documented progression If a tumor assessment was done on multiple days, use the earliest date for that visit.	Progressed
6	Death without documented progression	Date of death	Progressed
7	Documented progression or death after missing ≥ 2 consecutive postbaseline tumor assessments	Date of last adequate tumor assessment before missed assessments or date of first treatment, whichever is later	Censored

Note: Progression-free survival and associated outcome is determined by the earliest of the dates above, if more than 1 situation applies.

Time-to-response, DoR, DCR, and PFS will be assessed based on RECIST v.1.1. Exploratory analysis of TTR, DoR, and PFS may be conducted using irRECIST.

Overall survival (OS) is defined as time from the date of first treatment to the date of death from any cause. For each patient who is not known to have died as of the data inclusion cut-off date for a particular analysis, OS will be censored for that analysis at the date of last contact prior to the data-inclusion cut-off date (contacts considered in the determination of last contact date include AE date, lesion assessment date, visit date, and last known alive date).

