8.1. Efficacy

8.1.1. ***Efficacy Assessments at Baseline and during Study Treatment***

RECIST 1.1 ([Attachment 6](#)) will be applied as the primary measure for assessment of tumor response and date of disease progression. Local tumor imaging (investigator assessment with site radiological reading) will be used.

Tumor imaging should be performed by CT, which is preferred for the majority of patients, as the more commonly used modality. Magnetic resonance imaging (MRI) should only be used when CT is contraindicated or for imaging in the brain. The same imaging technique should be used for a patient throughout the trial. Imaging should include the chest, abdomen, and pelvis.

The subsections below describe in detail the tumor imaging and assessment measures at baseline and during study treatment (one or both study drugs, Section [4.1.3](#)).

8.1.1.1. **Baseline Tumor Imaging**

Initial tumor imaging at screening must be performed within 21 days prior to the date of enrollment (assignment to treatment) or within 28 days of the first dose of study treatment. The site study team must review screening images to confirm the patient has measurable disease per RECIST 1.1.

Scans performed as part of routine clinical management are acceptable for use as initial tumor imaging if they are of diagnostic quality and performed within protocol required time frame as described above.

8.1.1.2. **Tumor Imaging During Study Treatment**

During study treatment, tumor response will be assessed every 6 weeks (\pm 7 days) by investigator, with confirmatory assessment obtained at the next routine scheduled imaging time point (that is, after 6 weeks \pm 7 days). After 24 weeks, tumor assessment will be conducted every 12 weeks (\pm 7 days).

Per RECIST 1.1, partial or complete response should be confirmed by a repeat tumor imaging assessment not less than 4 weeks from the date the response was first documented. The tumor imaging for confirmation of response may be performed at the earliest 4 weeks after the first indication of response, or at the next scheduled scan (that is, 6 weeks \pm 7 days later), whichever is clinically indicated.

Continue to perform imaging until whichever of the following occurs first:

- disease progression confirmed by the second radiographic exam

- the start of new anticancer treatment
- withdrawal of consent
- death
- end of trial

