NOTE: Discontinuation of study treatment may be considered for patients who have attained a confirmed CR that have been treated for at least 24 weeks with study treatment and had at least 2 treatment cycles beyond the date when the initial CR was declared.

In determining whether or not the tumor burden has increased or decreased, study site investigators should consider all target lesions as well as non-target lesions (see Procedure Manual). Patients that are deemed clinically unstable are not required to have repeat tumor imaging for confirmation. If radiologic progression is confirmed by subsequent scan, then the patient will be discontinued from study treatment. If radiologic progression is not confirmed,

then the patient should resume or continue trial treatment and have their next tumor imaging according to the protocol schedule of every 6 weeks (\pm 7 days).

8.1.2. *Efficacy Assessments during Postdiscontinuation Follow-Up*

Postdiscontinuation follow-up during the study period will be conducted per the Time and Events Table ([Attachment 1](#)).

Tumor assessments may continue for patients who are withdrawn from the study for reasons other than disease progression every 6 to 12 weeks depending on standard of care.

8.1.3. *Efficacy Measures*

The objective response rate (ORR) is the proportion of enrolled patients who have received any amount of either study drug, have at least 1 postbaseline tumor image, and achieve a best overall response of complete response (CR) or partial response (PR). The ORR will be assessed based on RECIST 1.1 (Eisenhauer et al. 2009) and irRECIST.

Time-to-response (TTR) is the time from the date of first study treatment until the first evidence of a confirmed CR or PR, as defined in Section [8.1.1.3](#).

Duration of response (DoR) is defined only for responders (patients with a confirmed CR or PR). It is measured from the date of first evidence of a confirmed CR or PR to the date of objective progression or the date of death due to any cause, whichever is earlier. If a responder is not known to have died or have objective progression as of the data inclusion cutoff date, DoR will be censored at the date of the last complete objective progression-free disease assessment.

Disease Control Rate (DCR) is defined as the proportion of enrolled patients who have a best overall response of CR, PR, or stable disease (SD).

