Abbreviations: AE = adverse event; Att. = attachment; BTC = biliary tract cancer; CT = computed tomography; CTCAE = Common Terminology Criteria for Adverse Events; ECG = electrocardiogram; ECOG PS = Eastern Cooperative Oncology Group performance status; ERB = ethical review board; Gastric-GEJ= Gastric-Gastroesophageal Junction; ICF = informed consent form; MRI = magnetic resonance imaging; MUGA = multiple-gated acquisition; NSCLC = non-small cell lung cancer; PD = progressive disease; Prot. Ref. = protocol reference; Ram = ramucirumab; SAE= serious adverse event; TSH = thyroid-stimulating hormone.

FOOTNOTES Regarding Tumor Assessment:

- During treatment cycles, perform tumor assessment and imaging as follows: (i) every 6 weeks (± 7 days) for the first 6 months after enrollment, and (ii) every 12 weeks (± 7 days) thereafter. Perform as scheduled even if study treatment is delayed, except when tumor assessment and imaging are not feasible in the opinion of the investigator because of the patient's clinical status.
- If radiologic imaging verifies initial progressive disease (PD), tumor assessment should be repeated approximately 4 weeks later in order to confirm PD with the option of continuing study treatment while awaiting radiologic confirmation of progression (Section 8.1.1.3).
- During the short-term and long-term follow-up periods, for patients who discontinue study treatment without objectively measured PD, continue to perform tumor assessment and imaging every 6 to 12 weeks depending on standard of care.

Time and Events Table: Continued Access Period

	Continued Access Period			Notes
	Continued Access Treatment (21-day cycles)	Continued Access	Follow-Up	
				Day 1 and Day 8 assessments are performed only if study drug dosing is scheduled to occur on that day. Continued access follow-up begins 1 day after the patient and the investigator agree that the patient will no longer continue treatment in the continued access period and lasts approximately 30 days. Efficacy assessments will be performed at the investigator's discretion based on the standard of care.
Relative Day within a Cycle	Day 1	Day 8		
Procedures				
Weight	X			
Administer Ramucirumab				
BTC 8 mg/kg	X	X		
Gastric-GEJ 8 mg/kg	X	X		
Gastric-GEJ 10 mg/kg	X			
NSCLC 10 mg/kg	X			
Urothelial 10 mg/kg	X			
Administer Pembrolizumab 200 mg (fixed)				
All treatment cohorts	X			

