Progressive Disease (PD): At least a 20% increase in the sum of the diameters of target lesions, taking as reference the smallest sum on study (including the baseline sum if that is the smallest). In addition to the relative increase of 20%, the sum must also demonstrate an absolute increase of at least 5 mm. The appearance of 1 or more new lesions is also considered progression.

For equivocal findings of progression (for example, very small and uncertain new lesions; cystic changes or necrosis in existing lesions), treatment may continue until the next scheduled assessment. If at the next scheduled assessment, progression is confirmed, the date of progression should be the earlier date when progression was suspected.

Stable Disease (SD): Neither sufficient shrinkage to qualify for PR nor sufficient increase to qualify for PD, taking as reference the smallest sum diameters while on study.

Not Evaluable: When an incomplete radiologic assessment of target lesions is performed or there is a change in the method of measurement from baseline that impacts the ability to make a reliable evaluation of response.

Evaluation of Nontarget Lesions

Complete Response: Disappearance of all nontarget lesions and normalization of tumor marker level. All lymph nodes must be non-pathological or normal in size (<10mm short axis).

Non-CR/ non-PD: Persistence of 1 or more nontarget lesions and/or maintenance of tumor marker level above the normal limits.

Progressive Disease: Unequivocal progression of existing nontarget lesions. The appearance of 1 or more new lesions is also considered progression.

Not Evaluable: When a change in method of measurement from baseline occurs and impacts the ability to make a reliable evaluation of response.

Evaluation of Best Overall Response

The best overall response is the best response recorded from the start of the study treatment until the earliest of objective progression or start of new anticancer therapy, taking into account any requirement for confirmation. The patient's best overall response assignment will depend on the findings of both target and nontarget disease and will also take into consideration the appearance of new lesions. The Best Overall Response will be calculated via an algorithm using the assessment responses provided by the investigator over the course of the trial.

Time Point Response

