NSAIDs	yes	no	Chronic use of aspirin up to 325 mg/day is permitted. In addition, in certain medical situations, NSAIDs may be the best treatment option (for example, for pain management). Increased risk of bleeding should be considered by the treating physician and the patient.
Radiation therapy	no	no	Localized radiation therapy to a symptomatic, solitary lesion or to the brain may be allowed after consultation with the Sponsor.

Abbreviations: INR = international normalized ratio; NSAIDs = nonsteroidal anti-inflammatory drugs.

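### The SAP's best-overall-response window omits the protocol's stop at new anticancer therapy, so a response seen or confirmed after a later treatment could be counted in ORR

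*SAP*

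**What the plan says.** The SAP defines the window in a note under DCR in section 5.2.1.4: "Best overall response is the best response recorded from the start of treatment until disease progression, in the order of CR, PR, and SD". Two endpoints use it. ORR counts patients who "have at least 1 postbaseline tumor image, and achieve a best overall response of CR or PR", and DCR is "the proportion of treated patients achieving a best overall response of complete response (CR), partial response (PR), or stable disease (SD").

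Protocol Attachment 6 runs the window from the start of study treatment "until the earliest of objective progression or start of new anticancer therapy, taking into account any requirement for confirmation". It adds that best overall response is computed by algorithm from the investigator's assessments.

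Four protocol passages bear on whether scans after a new therapy can exist:

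- Section 8.1.1.2 (imaging during study treatment) lists "the start of new anticancer treatment" among the events that end imaging.
- Section 7.1 has a patient who needs another effective agent leave the study before that agent is introduced.
- Section 8.1.2 (post-discontinuation) says "Tumor assessments may continue for patients who are withdrawn from the study for reasons other than disease progression".
- The Attachment 1 footnote says, "for patients who discontinue study treatment without objectively measured PD, continue to perform tumor assessment and imaging every 6 to 12 weeks", with the interval depending on standard of care.

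The last two do not mention new therapy as a stop.

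**The concern.** In cohorts without a control arm, ORR is meant to describe the activity of ramucirumab plus pembrolizumab. If the window stays open after a patient moves to another treatment, shrinkage caused by that treatment can be recorded as the best response on study. A response first seen on the study drugs can also be confirmed by a scan taken under different therapy.

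Because best response is derived by algorithm, the wording that is programmed decides the result, and neither document describes a later step to remove such a scan. At stake are a possible upward shift in a secondary endpoint and an ORR that depends on which document the programmer follows. The SAP says that all efficacy endpoints will inform the next development steps, so the definition should be unambiguous.

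**Working it through.** **1. Is the stop restored elsewhere in the SAP?** I looked at the ORR, DCR, DoR and TTR definitions and the PFS rules in Table JVDF.3 (all in 5.2.1.4), the irRECIST variables (5.2.1.5) and the efficacy analyses (5.3.10). None ends response assessment at a new anticancer treatment. The note also omits the confirmation clause, although TTR and DoR refer to confirmed responses.

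**2. The two windows applied to the same patient (RECIST 1.1):**

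| Patient history | SAP note, read literally | Attachment 6 | ORR count | DCR count |
|---|---|---|---|---|
| SD on study drugs, both stopped without PD, new therapy, then PR with confirmation | PR | SD | +1 | 0 |
| PR first seen on study drugs, confirmed only after new therapy | PR | not a confirmed response | +1 | 0 if the patient qualifies as SD |
| No SD or better before new therapy and no PD, then SD | SD | not counted | 0 | +1 |
| PD before new therapy | window closed | window closed | 0 | 0 |

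The SAP window contains the Attachment 6 window. Best response is a maximum over the window, so a longer window can add a responder but cannot remove one. The direction for ORR is therefore upward or nil. DCR moves only in the third row.

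**3. irRECIST.** SAP 5.2.1.5 needs no confirmation for irORR and looks past an unconfirmed first progression. One scan would be enough, and no new-therapy cut-off is given.

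**4. The plan's own figures.** Take r as the smallest count with P(X ≥ r | n, null) ≤ 0.20, and power as P(X ≥ r | n, target):

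- n=25, null 10%: r=5, exact level 0.098; power at 20% is 0.579 (SAP Table JVDF.1: 57.9%).
- n=30, null 10%: r=5, exact level 0.176; power at 20% is 0.745 (stated 74.5%).
- n=25, null 30%: r=10, exact level 0.189; power at 45% is 0.758 (SAP Table JVDF.2: 75.8%).

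All twelve stated powers reproduce to within 0.1 point. They take every response as due to the study drugs, so restoring the stop changes no power and no sample size.

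**5. Size per patient** (planned cohort sizes from SAP 5.1.2):

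- 1/25 = 4.0 points (Cohorts A1, A2, C, D, E)
- 1/30 = 3.3 points (Cohorts A and B combined)
- 1/15 = 6.7 points (Cohort A or B alone)

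Example at n=25: 4 responders give 16% (exact 90% CI 5.7% to 33.0%); 5 give 20% (8.2% to 37.5%). Five is also the count at which the 10% null would be rejected in the power calculation, although the SAP says those ORR values are not decision criteria.

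**6. Frequency.** Neither document gives the share of patients who start another therapy before PD, or how often they would still be scanned. No cohort-level estimate can be derived from the documents.

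**The case against.** The strongest reply is that the protocol already prevents the problem. Section 8.1.1.2 ends imaging when new treatment starts. Its heading refers to study treatment, but chemotherapy and anticancer biologics are prohibited then (Attachment 7), so that stop has meaning mainly afterwards. Section 7.1 takes the patient off study before a new effective agent. The post-discontinuation texts are silent on new therapy rather than contrary, and one says only that assessments may continue. Also, protocol 9.2 describes the SAP as adding detail, the SAP assesses ORR by RECIST 1.1, and the note does not claim to replace Attachment 6.

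Much of this stands. It makes such scans uncommon, and it means the documents *could* give different ORRs, not that they will. It does not close the route. Section 8.1.2 expressly covers patients withdrawn from the study, Attachment 1 collects subsequent anticancer treatments in follow-up, and an imaging rule does not filter a scan that was taken anyway. The need for confirmation narrows the RECIST route but can itself be met by a later scan.

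Three stronger readings are tempting but not supported:

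- *DCR is inflated too.* In the typical case SD becomes PR, and SD already counts.
- *Irradiated lesions are part of the same fault.* Attachment 7 says "Localized radiation therapy to a symptomatic, solitary lesion or to the brain may be allowed after consultation with the Sponsor", and a reader might infer that the SAP lets such shrinkage through. Neither document says how a target lesion irradiated on study is evaluated, so this is not a difference between them and is a separate question.
- *The size can be estimated from cited rates.* Combining the 10.5% adverse-event discontinuation on single-agent ramucirumab with the 28% ORR for ramucirumab plus paclitaxel gives 25 × 0.105 × 0.28 = 0.7 patients. But the first rate is not stopping both drugs without PD, as 7.1 requires here. The second comes from one tumour type and a ramucirumab regimen, and Cohorts A2 and E enrol patients who cannot have or refuse standard first-line chemotherapy. Counting every such patient as a false responder is less supportable still.

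**Conclusion.** The mismatch is real: the SAP window ends only at progression, while the protocol window also ends at new anticancer therapy and takes confirmation into account. Read literally, the SAP can only raise ORR relative to Attachment 6. The amount per affected patient is fixed by cohort size, as shown above.

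The number affected is not in the documents. My judgement is fewer than one patient per cohort, which assumes that sites mostly follow 8.1.1.2 and 7.1. Taking zero to one patient as the range, the shift is 0 to 4.0 points at n=25, 0 to 3.3 at n=30 and 0 to 6.7 at n=15.

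The primary safety objective, the sample size and the stated power are untouched. This is a minor alignment correction to a secondary endpoint, not evidence that the reported ORR will be materially biased.

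**What to change.** Replace the note in SAP 5.2.1.4 with the Attachment 6 window: best response from the start of study treatment "until the earliest of objective progression or start of new anticancer therapy, taking into account any requirement for confirmation". This also restores the confirmation clause. In 5.2.1.5, apply the same new-therapy cut-off to best response by irRECIST, leaving its own rule on confirmation as it is.

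The cost is one replaced sentence, one added sentence and a filter on the start date of subsequent therapy. Attachment 1 already provides for collecting subsequent anticancer treatments, and SAP 5.3.5 already summarizes post-discontinuation therapy. No new data, patients or power calculations are needed. Relative to a literal reading of the current note, ORR can only stay the same or fall.

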5.2.1.5. Efficacy Analysis Variables (irRECIST)

For Study JVDF, RECIST v.1.1 will be adapted to account for the unique tumor response characteristics seen with treatment of pembrolizumab (irRECIST). Immune-related RECIST will be applied as detailed in the study protocol, and the resulting data will be included in the clinical database.

Immune-related objective response rate (irORR) is defined as the proportion of treated patients achieving a best overall response of PR or CR per irRECIST, particularly, the best

overall response by irRECIST closely related to confirmed response by RECIST. Immune-related ORR further captures responses after unconfirmed PD and does not require confirmation. For example:

- If the best response by RECIST v.1.1 is CR, then the best response by irRECIST is CR.
- If the best response by RECIST v.1.1 is PR, SD, or PD, the best response by irRECIST is the best response over the initial assessment (prior to PD by RECIST v.1.1) and the confirmation stage.

Overall, the best response by irRECIST should be the same or better than the best response by RECIST v.1.1 criteria. In addition, patients who do not have any postbaseline tumor response assessments for any reason are considered non-evaluable and will be included in the denominator when calculating the response rate.

[figure not shown]
Immune-related progression-free survival (irPFS) is defined as the date from the treatment started date to the time of PD assessed by irRECIST.

- If the initial PD is confirmed, then the date of immune-related (ir)PD is the initial PD date by RECIST v.1.1.
- If the initial PD is unconfirmed, then the date of irPD is the date of second PD.

[figure not shown]
Duration of response by irRECIST is defined from the date of first documented irCR or irPR (responder) to the date of irPD or the date of death due to any cause, whichever is earlier.

Graphic Example:

Scenario 1: The initial PD is confirmed at the next scan (consecutive PD). The efficacy variables by irRECIST and RECIST are the same.

Scenario 2: The initial PD is not confirmed at the next scan (non-consecutive PD). The efficacy variables by irRECIST and RECIST v.1.1 are different.

In addition, the best response after initial PD may be listed. Other efficacy analysis based on irRECIST may be performed for exploratory analysis.

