The main goal of confirmation of objective response in clinical trials is to avoid overestimating the response rate observed. The confirmation of response is particularly important in *nonrandomized trials* where response (CR/PR) is the primary end point. In this setting, to be assigned a status of PR/CR, changes in tumor measurements must be confirmed by repeat assessments that should be performed no less than 4 weeks after the criteria for response are first met. To confirm a response of CR, a full assessment of all target and nontarget lesions that were present at baseline must occur, including those measured by bone scan. To confirm a PR or SD, a full assessment of target lesions that were present at baseline must occur; assessment of nontargets is not required.

However, in *randomized trial* (Phase 2 or 3) or studies where SD or progression is the primary endpoints, confirmation of response is not required. But, elimination of the requirement may increase the importance of central review to protect against bias, in particular of studies which are not blinded.

In the case of SD, follow-up measurements must have met the SD criteria at least once after start of treatment at a minimum interval not less than 6 weeks measured from **[first dose]**.

Duration of Overall Response

The duration of overall response is measured from the time measurement criteria are first met for CR or PR (whichever is first recorded) until the first date that disease is recurrent or objective progression is observed (taking as reference for PD the smallest measurements recorded on study).

The duration of overall CR is measured from the time measurement criteria are first met for CR until the first date that recurrent disease is objectively documented.

Duration of Stable Disease

Stable disease is measured from the start of the treatment (in randomized trials, from date of randomization) until the criteria for objective progression are met, taking as reference the smallest sum on study (if the baseline sum is the smallest, that is the reference for calculation of PD).

Independent Review of Response and Progression

When objective response (CR + PR) is the primary end point, and when key drug development decisions are based on the observation of a minimum number of responders, it is recommended that all claimed responses be reviewed by an expert(s) independent of the study. If the study is a randomized trial, ideally reviewers should be blinded to treatment assignment.

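### irORR may count unconfirmed responses while RECIST 1.1 response is confirmed, so the two rates are not like for like, and the rule conflicts with the SAP's own Scenario 1

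*SAP*

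**What the plan says.** **irRECIST side.** SAP 5.2.1.5 defines irORR as the proportion of treated patients whose best response by irRECIST is PR or CR. It adds: "Immune-related ORR further captures responses after unconfirmed PD and does not require confirmation". Unless the RECIST best response is already CR, the irRECIST best response is taken over the scans before RECIST progression together with the confirmation stage. The section expects it never to be worse than the RECIST best response.

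**RECIST side.** Protocol 8.1.1.2 says: "Per RECIST 1.1, partial or complete response should be confirmed by a repeat tumor imaging assessment not less than 4 weeks from the date" of first documentation. Attachment 6 makes best overall response subject to any confirmation requirement. SAP 5.2.1.4 makes DoR "defined only for responders (patients with a confirmed CR or PR"), and TTR likewise runs to a confirmed response. SAP 5.2.1.5 describes the irRECIST response as "overall response by irRECIST closely related to confirmed response by RECIST". The ORR definition in SAP 5.2.1.4 asks only that patients "have at least 1 postbaseline tumor image, and achieve a best overall response of CR or PR", and its note on best overall response sets no confirmation condition: "Best overall response is the best response recorded from the start of treatment until disease progression, in the order of CR, PR, and SD".

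**Scenario 1.** The same SAP section says that when the initial PD is confirmed at the next scan, the efficacy variables under the two criteria are identical.

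**The concern.** The irRECIST adaptation is justified in protocol 8.1.1.3 by responses that appear after an initial rise in tumor burden or after new lesions. That is a reason to extend the response window past a first, unconfirmed PD. It is not a reason to drop confirmation of response, and that protocol section gives a confirmation rule for progression only.

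As worded, irORR changes the window and the standard of evidence together. A reader who sees irORR above ORR cannot tell how much comes from late immune-type responses and how much from one-scan responses that did not hold. Attachment 6 says the purpose of confirmation is to avoid overestimating the response rate. That purpose is relevant to an open-label trial with local reading and no comparator within a cohort. A second problem is practical: the no-confirmation sentence and Scenario 1 can lead two programmers to different irORRs from the same data.

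**Working it through.** **1. The plan's own ORR figures.** The only ORR calculation in the documents is the power table (SAP Tables JVDF.1 and JVDF.2; one-sided 0.20). Method: find the smallest r with P(X ≥ r | n, p0) ≤ 0.20, then power = P(X ≥ r | n, p1), exact binomial.

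- n = 25, 10% vs 20%: r = 5, error 9.8%, power 57.93% (stated 57.9%).
- n = 30, 10% vs 25%: r = 5, error 17.5%, power 90.21% (stated 90.2%).
- n = 25, 35% vs 55%: r = 12, error 12.5%, power 81.73% (stated 81.7%).

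All twelve stated powers reproduce. None is wrong, and none is a figure for irORR.

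**2. Direction.** On one denominator, confirmed irORR responders are a subset of all irORR responders. So unconfirmed irORR ≥ confirmed irORR.

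**3. Where the two rules collide.** Take a patient with PR at one scan, PD at the next, and PD confirmed at the repeat scan.

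| Rule | Counted as responder? |
|---|---|
| RECIST ORR with confirmation (protocol 8.1.1.2) | No |
| irORR, no-confirmation sentence applied to all responses | Yes |
| irORR, Scenario 1 (same as RECIST) | No |

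The second and third rows come from the same SAP section.

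**4. Size.** The documents give no failure rate for confirmation. Assume a share u of first responses fails, all of these count in irORR, and there are no late responses. Then irORR = confirmed ORR / (1 − u). With confirmed ORR = 20%, or 5/25:

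| u (assumed) | irORR if all failures count | Expected responders in 25 | irORR if half of the failures are removed by Scenario 1 | irORR if all are removed |
|---|---|---|---|---|
| 10% | 0.20/0.90 = 22.2% | 5.6 | 21.1% | 20% |
| 20% | 0.20/0.80 = 25.0% | 6.3 | 22.5% | 20% |
| 30% | 0.20/0.70 = 28.6% | 7.1 | 24.3% | 20% |

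The half share is also an assumption. The third-column excess is 0.20 × u/(1 − u), at most 8.6 points or about 2 patients in 25.

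**5. Against sampling error.** One responder in 25 is 4 points: 4/25 = 16% (exact 90% CI 5.7% to 33.0%) becomes 5/25 = 20% (8.2% to 37.5%). The shift is small beside the interval, but it always goes in one direction.

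**6. Against the power reference, as illustration only.** For n = 25, a 10% null and r = 5, the chance of reaching r with a confirmed rate of 10% is 9.8%. If irORR were used instead, with rate 0.10/(1 − u), it would be 13.7%, 19.5% and 28.1% for u = 10%, 20% and 30%. These are upper values, because Scenario 1 would reduce them.

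**7. Denominators.** The ORR sentence in SAP 5.2.1.4 can be read as excluding patients without a postbaseline image; irORR in 5.2.1.5 includes them; SAP 5.3.10 divides both rates by patients assessable at baseline. With 5 responders and 2 unimaged patients among 25, ORR could be 5/23 = 21.7% while irORR is 5/25 = 20.0%. So the reported irORR need not exceed the reported ORR.

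**The case against.** The strongest reply is that the sentence is narrower than it looks. The waiver of confirmation shares a sentence with responses after unconfirmed PD and may apply only to those. Scenario 1 supports that reading, and the drawings that accompany the scenarios, which are missing from the text I worked from, may settle it. This stands as a reason to call the text ambiguous. It does not remove the problem: a response after unconfirmed PD would still be accepted on one scan, and Scenario 1 does not cover a failed one-scan response in a patient without confirmed PD.

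Other points also stand:

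- Attachment 6 does say "changes in tumor measurements must be confirmed by repeat assessments", but for nonrandomized trials with response as the primary endpoint. Here safety is primary and response secondary, so the stated purpose carries over but the mandatory wording does not squarely apply.
- The SAP's ORR sentence does not say confirmed. The requirement is strongly implied by the other places, not explicit there.
- A reader might infer that irORR is inflated. The documents do not show this: the failure rate is unknown, Scenario 1 may remove part of the effect, and the denominators differ.
- A reader might also infer that a cohort could pass a response threshold on irORR alone. Protocol 9.1 and SAP 5.1.2 say the ORR values are not decision criteria, and 5/25 already reaches the count of 5 for a 10% null.
- Neither document plans to interpret irORR minus ORR. RECIST 1.1 is the primary response measure, both rates are reported, and DoR is limited to confirmed responders.

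**Conclusion.** The concern holds as a mismatch of definitions and an unresolved conflict within SAP 5.2.1.5. On a common denominator, irORR as worded cannot be lower, and may be higher, than a confirmed irORR, and a raw irORR-to-ORR difference has no single interpretation. The upper bound for a confirmed 20% is 22% to 29%, before any genuine late responses. It rests on the assumptions that 10% to 30% of first responses fail confirmation and that every failure counts. If Scenario 1 governs, the figure is lower. No stated power figure changes.

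The consequence is moderate. irORR is a secondary endpoint, but all efficacy endpoints are to inform the next development steps, so the rate should mean one thing. The repair is worth making because it is cheap.

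**What to change.** Amend the SAP as follows:

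- In 5.2.1.4, state that RECIST 1.1 ORR counts confirmed CR or PR.
- In 5.2.1.5, report irORR with the same confirmation, at least 4 weeks after first documentation, still counting confirmed responses that follow an unconfirmed PD.
- Show the unconfirmed irORR beside it, labelled as unconfirmed, with all three rates on the same denominator.
- Reconcile the no-confirmation sentence with Scenario 1, saying how a one-scan response followed by confirmed PD is classified.
- Make the listing of best response after initial PD, now optional, a planned output, so that late responses can be seen separately.

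Cost: SAP wording, one extra table row, a listing the SAP already allows for, and possibly a slightly lower irORR. Protocol 8.1.1.2 already provides for confirmatory imaging, so no added visits should be needed.
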